9.12.7 Skin irritation assessment

The number and percentages of subjects in each score of skin irritation assessment will be summarized by visits, baseline in DSP-5423P application period, each visit, LOCF endpoint, and also maximum score throughout the DSP-5423P post-baseline period. Skin irritation assessment scores will be listed.

9.12.8 Subgroup analysis for safety

The summary of TEAE and treatment-related TEAE and also their summary by SOC/PT will be presented by subgroups. The subgroups include Sex, Age(years), Duration of illness (years), and Hospitalization status at Screening defined as below. Subjects with missing data for any subgroup categories will not be included subgroup analysis without setting ‘missing’ category.

Sex: Male, Female

Age (years): < 65, \geq 65

Duration of illness (years): < 5, \geq 5 to < 10, \geq 10 to < 20, \geq 20, Unknown

Hospitalization status at Screening: Inpatient, Outpatient

9.13 Analysis of Other endpoints

All analysis of other endpoints will be conducted based on Safety population by each cohort and cohort total.

9.13.1 DAI-10

DAI-10 item scores will be summarized at baseline of DSP-5423P application period, each visit, and LOCF endpoints using number and percentage of subjects. For DAI-10 total score, the number and percentage of subjects and also descriptive summaries in change from baseline of DSP-5423P application period will be provided by each visit including LOCF endpoints. DAI-10 will be listed.

9.13.2 EQ-5D

For EQ-5D item scores, the number and percentage of subjects by scores will be summarized at baseline of DSP-5423P application period, each visit and LOCF endpoint. Observed value and change from baseline of DSP-5423P application period in EQ-5D Index value (QS.QTESTCD=EQTOT) will be summarized by each visit and LOCF endpoints. EQ-5D will be listed.

9.13.3 Questionnaire on dosage form

The number and percentage of subjects by each question at LOCF endpoint will be summarized. Summary will be repeated for subjects who completed the study, discontinued the study, and overall. Questionnaire on dosage form will be listed.

9.14 Pharmacokinetic analysis

9.14.1 Plasma drug concentration

Summary statistics of plasma concentrations of blonanserin and metabolites specified in section 7.4.2, will be calculated by visits for each cohort and cohort total. Summary statistics will include n, Mean, SD, Min, Median, Max, CV%, Geometric Mean and Geometric CV%. This analysis will be repeated by visits, cohorts including cohort total, the latest dose prior to the PK sampling (ie, 40, 60, or 80 MG), and the latest application site (abdomen, back, chest, overall). For DSP-5423(tablet) administration period in Cohort 1, this analysis will also be repeated by fasting status, fasting, non-fasting and overall. The BLQ will not be included in the summary statistics.

Additionally, Summary statistics of the ratio of plasma concentration of metabolites to blonanserin (ie, M1/blonanserin) will be calculated by visits for each cohort and cohort total.

Plasma drug concentration and the ratio of plasma concentration of metabolites to blonanserin will be listed.

9.14.2 Subgroup analysis

Summary statistics of plasma concentration of blonanserin, and metabolites will also be summarized by subgroup. Subgroups will include sex and age group.

Sex: Male; Female

Age (years): < 65; ≥ 65

10. Appendix

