4.2 Study Conduct Rationale

In the clinical study in Japanese healthy adults, 1, 2, or 3 patches of DSP-5423P 32 mg/40 cm² were applied to 9 patients each for 24 hours. In addition, 2 patches of DSP-5423P 32 mg/40 cm² were

applied to 9 patients once daily for 10 days. The results showed that the plasma blonanserin concentration increased depending on the number of patches applied and that the steady state was nearly reached after repeated administration for 7 days.

A new patch formulation, DSP-5423P 20 mg/40 cm² was prepared. Pharmacokinetics, after the application of a single patch, were compared between these 2 patch formulations. The results showed that a comparable amount of blonanserin absorption was obtained with these 2 patch formulations. Therefore, the new formulation, DSP-5423P 20 mg/40 cm² was used in the following studies.

The phase 2 study of DSP-5423P was conducted in patients with schizophrenia to determine the recommended doses for phase 3 studies. Striatal dopamine D₂ receptor occupancy and plasma drug concentrations after application of DSP-5423P at doses of 10 to 80 mg/day for 2 weeks were compared with results obtained after administration of DSP-5423 (tablet formulation of blonanserin). The results suggest that DSP-5423P 40 mg/day and 80 mg/day may be comparable to DSP-5423 (tablet) 8 mg/day and 16 mg/day, respectively. Since the clinical efficacy of antipsychotics reportedly correlates with dopamine D₂ receptor occupancy^{ref 7, 8}, DSP-5423P at doses of 40 and 80 mg/day is expected to demonstrate efficacy corresponding to that of DSP-5423 (tablet) at doses of 8 and 16 mg/day, respectively. In clinical studies of DSP-5423P in healthy adult volunteers or subjects with schizophrenia, no clinically significant adverse events have been reported at doses up to 80 mg, demonstrating tolerability on the skin of application sites.

Considering these results, a phase 3 confirmatory study is currently being conducted in a randomized double-blind, placebo-controlled, parallel-group manner to confirm the superiority to placebo in order to evaluate the efficacy and safety of DSP-5423P.

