10.2 Dose adjustment criteria

The DSP-5423P dose can be increased or reduced by 20 mg/day at each adjustment within a range of 40 mg/day, 60 mg/day or 80 mg/day according to the following dose adjustment criteria. The DSP-5423 (tablet) dose can be increased or reduced by 4 mg/day at each adjustment within a range of 8 mg/day, 12 mg/day or 16 mg/day according to the following dose adjustment criteria.

Regulatory Assessment timing

- When the CGI-S score is between 4 and 7 and when no safety concerns arise, the DSP-5423P/DSP4323 (tablet) dose should be increased.
- When the CGI-S score is 3 or lower with no safety concerns and when the Investigator expects further efficacy of DSP-5423P/DSP4323 (tablet), the DSP-5423P/DSP4323 (tablet) dose can be increased.

As necessary

- When the Investigator considers a higher dose of DSP-5423P/DSP4323 (tablet) to be necessary due to insufficient efficacy, the DSP-5423P/DSP4323 (tablet) dose can be increased.
- When the Investigator considers a lower dose of DSP-5423P/DSP4323 (tablet) to be necessary due to the AEs, the DSP-5423P/DSP4323 (tablet) dose can be reduced.

PANSS and CGI-S should be evaluated before the dose adjustment at each unscheduled visit (Section 11.2 Efficacy Assessments). DIEPSS should be evaluated as well as PANSS and CGI-S when the DSP-5423P/DSP4323 (tablet) dose is reduced due to extrapyramidal symptoms (Section 11.3 Safety Assessments).

After the dose adjustment, the Investigator will record the reason for the dose adjustment in the CRFs. The DSP-5423P/DSP4323 (tablet) dose should not be changed for at least 1 week in principle, after the dose adjustment.

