If the dose of the prior antipsychotics exceeds 12.0 mg/day (haloperidol equivalent), washout period will be arranged. First, the dose is reduced to 12.0 mg/day or less, then down-titration would be done as needed. After termination of the prior antipsychotics, to initiate the administration of the DSP-5423 (tablet).

[figure not shown]
Washout period should be up to 4 weeks (28 days) from the screening.

** The registration procedure is presented in section 10 in the protocol.

4.3.2 Cohort 2

Cohort 2 consists of 2 period: DSP-5423P treatment period (52 weeks) and follow-up period (1-2 weeks). During the DSP-5423P treatment period, DSP-5423P will be applied once daily for 52 weeks. The study drug will be applied to the subject's back, chest, or abdomen. The initial dose of DSP-5423P will be 40 mg/day. DSP-5423P will be applied as flexible dose (40, 60, 80 mg/day) according to the dose adjustment criteria. Prior to initiation of DSP-5423P treatment period, a washout period (up to 4 weeks) will be arranged according to the dose of prior antipsychotics (haloperidol equivalent).

Figure 2 Study schematic (cohort 2).

* If the dose of the prior antipsychotics is 12.0 mg/day or less (haloperidol equivalent), to initiate the application of the DSP-5423P after termination of the prior antipsychotics. Washout period may be arranged and down-titration would be done as needed prior to termination.

If the dose of the prior antipsychotics exceeds 12.0 mg/day (haloperidol equivalent), washout period will be arranged. First, the dose is reduced to 12.0 mg/day or less, then down-titration would be done as needed. After termination of the prior antipsychotics, to initiate the administration of the DSP-5423P.

Washout period should be up to 4 weeks (28 days) from the screening.

** The registration procedure is presented in section 10 in the protocol.

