Table 14.3.6.1	Electrocardiogram Parameters – DSP-5423P Treatment Phase	Safety Population
Table 14.3.6.2	Electrocardiogram Parameters – DSP-5423 (tablet) Treatment Phase	Subjects treated with DSP-5423 (tablet)
Table 14.3.6.3	Electrocardiogram Abnormality – DSP-5423P Treatment Phase	Safety Population
Table 14.3.6.4	Markedly Abnormal Post-Baseline Values - Electrocardiogram – DSP-5423P Treatment Phase	Safety Population
Table 14.3.7.1	Drug-Induced Extrapyramidal Symptom Scale (DIEPSS) Total Score – DSP-5423P Treatment Phase	Safety Population
Table 14.3.7.2	Drug-Induced Extrapyramidal Symptom Scale (DIEPSS) Total Score – DSP-5423 (tablet) Treatment Phase	Subjects treated with DSP-5423 (tablet)
Table 14.3.7.3	Drug-Induced Extrapyramidal Symptom Scale (DIEPSS) Symptom Scores – DSP-5423P Treatment Phase	Safety Population
Table 14.3.7.4	Drug-Induced Extrapyramidal Symptom Scale (DIEPSS) Symptom Scores – DSP-5423 (tablet) Treatment Phase	Subjects treated with DSP-5423 (tablet)
Table 14.3.8.1	Columbia Suicide Severity Rating Scale (C-SSRS) Suicidal Ideation	Safety Population
Table 14.3.8.2	Columbia Suicide Severity Rating Scale (C-SSRS) Suicidal Behavior	Safety Population
Table 14.3.8.3	Columbia Suicide Severity Rating Scale (C-SSRS) Incidences of Suicidality	Safety Population
Table 14.3.8.4	Columbia Suicide Severity Rating Scale (C-SSRS) Emergence of Suicidality – DSP-5423P Treatment Phase	Safety Population
Table 14.3.9	Skin Irritation Assessment – DSP-5423P Treatment Phase	Safety Population
Table 14.4.1	Drug Attitude Inventory-10 (DAI-10) Total Score – DSP-5423P Treatment Phase	Safety Population

No	Title	Population
Table 14.4.2	Drug Attitude Inventory-10 (DAI-10) – DSP-5423P Treatment Phase	Safety Population
Table 14.4.3	Drug Attitude Inventory-10 (DAI-10) Total Score Compared to Baseline Assessment – DSP-5423P Treatment Phase	Safety Population
Table 14.4.4	EuroQol-5 Dimension (EQ-5D) Index Value – DSP-5423P Treatment Phase	Safety Population
Table 14.4.5	EuroQol-5 Dimension (EQ-5D) – DSP-5423P Treatment Phase	Safety Population
Table 14.4.6	Questionnaire for Formulation – DSP-5423P Treatment Phase	Safety Population
Table 14.5.1.1	Plasma Concentration of Blonanserin and Metabolites	PK Analysis Population
Table 14.5.1.2	Ratio of Plasma Concentration of Metabolites to Blonanserin	PK Analysis Population
Table 14.5.2.1	Plasma Concentration of Blonanserin and Metabolites by Sex	PK Analysis Population

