Table 14.5.2.2	Plasma Concentration of Blonanserin and Metabolites by Age	PK Analysis Population
Table 14.5.3	Plasma Concentration of Blonanserin and Metabolites by Most Recent Dose and Administration Site	PK Analysis Population
Listing 16.2.1.1	Patients Who Discontinued Study Treatment – DSP-5423 (tablet) Treatment Phase	All Patients
Listing 16.2.1.2	Patients Who Discontinued Study Treatment – DSP-5423P Treatment Phase	All Patients
Listing 16.2.1.3	Patient Disposition	All Patients
Listing 16.2.1.4	Analysis Population	All Patients
Listing 16.2.2	Important Protocol Deviations	All Patients
Listing 16.2.3	Patients Who Excluded from Efficacy Analysis	All Patients
Listing 16.2.4.1	Demographics and Baseline Characteristics	All Patients
Listing 16.2.4.2	Psychiatric History	All Patients
Listing 16.2.4.3	Concomitant Diseases	All Patients
Listing 16.2.4.4	Prior Medications	All Patients

No	Title	Population
Listing 16.2.4.5	Concomitant Medications Used in DSP-5423 (tablet) Treatment Phase	All Patients
Listing 16.2.4.6	Concomitant Medications Used in DSP-5423P Treatment Phase	All Patients
Listing 16.2.5.1	Treatment Compliance	All Patients
Listing 16.2.5.2	Treatment Exposure – Mean Daily Dose and Cumulative Dose	All Patients
Listing 16.2.5.3	Treatment Exposure	All Patients
Listing 16.2.5.4	Plasma Concentration of Blonanserin and Metabolites	All Patients
Listing 16.2.6.1	Positive and Negative Syndrome Scale (PANSS) – Total Score and Subscale Scores	All Patients
Listing 16.2.6.2	Clinical Global Impression-Severity of Illness (CGI-S)	All Patients
Listing 16.2.6.3	Time to All-Cases Treatment Discontinuation – DSP-5423P Treatment Phase	All Patients
Listing 16.2.7	Coding of Adverse Events by Medical Dictionary for Regulatory Activities (MedDRA)	-
Listing 16.2.7.1	Adverse Events	All Patients
Listing 16.2.7.2	Adverse Events Leading to Death	All Patients
Listing 16.2.7.3	Serious Adverse Events	All Patients
Listing 16.2.7.4	Adverse Events Leading to Treatment Discontinuation	All Patients
Listing 16.2.7.5	Extrapyramidal Adverse Events	All Patients
Listing 16.2.7.6	Adverse Events Related to Skin	All Patients
Listing 16.2.7.7	Adverse Events in DSP-5423 (tablet) Treatment Phase	All Patients
Listing 16.2.7.8	Narrative of Serious Adverse Events	-
Listing 16.2.8.1	Clinical Laboratory Data – Blood Chemistry	All Patients
Listing 16.2.8.2	Clinical Laboratory Data – Hematology	All Patients
Listing 16.2.8.3	Clinical Laboratory Data – Urinalysis	All Patients

No	Title	Population

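### The planned sex and age summaries of plasma concentration take no account of dose, which is flexible over a two-fold range; dose-normalised rows should be added

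*SAP*

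**What the plan says.** SAP 9.14.2 plans the subgroup summaries in two sentences: "Summary statistics of plasma concentration of blonanserin, and metabolites will also be summarized by subgroup. Subgroups will include sex and age group". The groups are male and female, and under 65 and 65 or over. The table list in SAP 10.2 matches: Table 14.5.2.1 is "Plasma Concentration of Blonanserin and Metabolites by Sex" and Table 14.5.2.2 is "Plasma Concentration of Blonanserin and Metabolites by Age".

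Dose enters the PK plan in one place. SAP 9.14.1 repeats the main summary by visit, cohort, "the latest dose prior to the PK sampling (ie, 40, 60, or 80 MG), and the latest application site". That becomes a separate table, 14.5.3, which is not crossed with sex or age. Neither the derived variables in SAP 8.2 nor section 9.14 defines a dose-normalised concentration.

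On dosing, SAP 4.3 states: "DSP-5423P will be applied as flexible dose (40, 60, 80 mg/day) according to the dose adjustment criteria". The tablet in cohort 1 is likewise flexible at 8, 12 or 16 mg/day. Protocol 10.2 ties dose to clinical state: "When the CGI-S score is between 4 and 7 and when no safety concerns arise, the DSP-5423P/DSP4323 (tablet) dose should be increased". It also allows a reduction because of adverse events. Protocol 4.2 reports from a study in healthy adults that "plasma blonanserin concentration increased depending on the number of patches applied".

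The doses of the last two patch applications, or last two tablet administrations, before each PK sample are recorded (Protocol 11.4, SAP 7.4.2).

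**The concern.** A table of concentrations by sex or age will be read as showing whether exposure differs between those groups. In a fixed-dose study that reading is fair. Here each subject's concentration reflects both exposure per mg and the dose the investigator has settled on, and the dose depends on symptoms and tolerability. A difference in dosing between groups can look like a PK difference or conceal one.

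The dosing rule also supplies a mechanism for concealment. If one group had higher exposure per mg and more adverse events as a result, its members could be held at, or moved to, lower doses. The raw concentrations would then be drawn together. In addition, cohort 1 starts the patch at 40, 60 or 80 mg according to the final tablet dose (Protocol Table 8), whereas cohort 2 starts at 40 mg, so a cohort total can combine different dose histories.

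What is at stake is the interpretability of two descriptive tables. No test, sample size or primary conclusion depends on them.

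**Working it through.** The plan gives no figure on this point, so there is none to reproduce. The check has two parts.

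**1. Is dose handled anywhere within sex or age?**

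- SAP 9.14.2: sex and age only.
- SAP 9.14.1 and Table 14.5.3: latest dose and application site, with no sex or age.
- SAP 8.2: dose summaries and a metabolite-to-parent ratio, but no concentration per mg.
- SAP 10.2: three separate tables (14.5.2.1, 14.5.2.2, 14.5.3), none crossing dose with sex or age.

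So dose is not handled within the sex and age summaries.

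**2. How large could the effect be?**

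Inputs from the documents: dose levels 40, 60 and 80 mg/day, so the extreme dose ratio is 80/40 = 2 (tablet: 16/8 = 2). Assumed, because the documents do not give them: the dose mix in each group, concentration proportional to dose, and, within a group, exposure per mg unrelated to dose.

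With k = mean exposure per mg and D = mean dose in groups A and B:

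- raw ratio B/A = (k_B / k_A) × (D_B / D_A)
- dose-normalised ratio B/A = k_B / k_A

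Using assumed mean doses:

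- No true difference, 50 v 65 mg: 50/65 = 0.77.
- True ratio 1.3, 50 v 65 mg: 1.3 × 50/65 = 1.00.
- True ratio 1.3, 45 v 65 mg: 1.3 × 45/65 = 0.90.
- True ratio 1.3, 60 v 65 mg: 1.3 × 60/65 = 1.20.

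Using assumed shares at 40/60/80 mg, with no true difference:

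| Group A | Group B | Mean dose A | Mean dose B | Arithmetic ratio B/A | Geometric ratio B/A |
|---|---|---|---|---|---|
| 30/30/40% | 30/30/40% | 62 | 62 | 1.00 | 1.00 |
| 30/30/40% | 40/30/30% | 62 | 58 | 0.94 | 0.93 |
| 20/20/60% | 50/25/25% | 68 | 55 | 0.81 | 0.80 |
| 10/20/70% | 70/20/10% | 72 | 48 | 0.67 | 0.66 |
| all 80 mg | all 40 mg | 80 | 40 | 0.50 | 0.50 |

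For the second row, the arithmetic means are 0.30×40 + 0.30×60 + 0.40×80 = 62 and 0.40×40 + 0.30×60 + 0.30×80 = 58, and 58/62 = 0.94. The geometric means are 59.6 and 55.6, and 55.6/59.6 = 0.93. Dose-normalising gives 1.00 in every row under the same assumptions. The first row shows that with equal dose mixes the raw table is not distorted at all.

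**The case against.** The strongest case against has five parts.

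- **The tables are descriptive and PK is a secondary objective.** No test, model or statement about clearance is planned, and the concentrations actually reached under flexible dosing are worth reporting. This stands. It is a reason to keep the raw tables, not a reason to leave out a dose-normalised version.
- **No imbalance is shown.** A reader might infer that older subjects, or one sex, will sit at lower doses and that a real exposure difference will be hidden. The documents do not support that: they give no dose distribution by sex or age and no expected exposure difference. The dosing rule makes an imbalance possible, no more. The two-fold limit needs one group wholly at 40 mg and the other wholly at 80 mg.
- **These may not be the study's only look at the question.** Protocol section 15 and SAP section 1 allow for a separate PK or PK-PD analysis under its own plan, and individual concentrations are listed. This also stands. But the separate analysis is conditional, its plan is not among the documents, and a listing is not a dose-adjusted summary. What can be said is that these are the only sex and age PK summaries planned in this SAP.
- **Proportionality has thin support.** The Protocol 4.2 finding comes from one to three patches of an earlier 32 mg formulation and gives no slope. Absorption from a single new patch was reported as comparable. This shows that dose matters, not by how much.
- **SAP 9.14.2 might be read as inheriting the dose breakdown of 9.14.1.** The wording permits that reading, but the separate table titles make it the weaker one.

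**Conclusion.** The omission is clear from the text. As written, the sex and age summaries cannot separate a difference in dose from a difference in exposure per mg. Whether that matters in the data depends on whether dose mixes differ between the groups, which is unknown. Under assumed mixes and proportionality, the raw ratio with no true difference ranges from 1.00 (identical mixes) through 0.93 to 0.66 (geometric), with 0.50 as the extreme. All of these sizes are illustrative.

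This is a modest point. It does not touch the primary safety objective, and it does not establish that an exposure difference exists or would be missed. It is worth making because the remedy is cheap and makes the two tables interpretable.

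**What to change.** Keep Tables 14.5.2.1 and 14.5.2.2 as planned and add dose-normalised rows:

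- In SAP 8.2, define dose-normalised concentration as the plasma concentration divided by the latest recorded dose before sampling: the patch dose for patch-phase samples and the tablet dose for tablet-phase samples. Because tablets are taken twice daily, state whether the tablet dose is per administration or per day.
- In SAP 9.14.2, add one sentence saying that the sex and age summaries present both raw and dose-normalised values for blonanserin and metabolites.

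**Cost.** One derived variable, one sentence and extra rows in two tables. The doses are already recorded with each PK sample, and no clinical procedure changes.

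**Limits.** Normalisation assumes approximate dose proportionality. Table 14.5.3 allows that to be checked for the patch; SAP 9.14.1 names only the 40, 60 and 80 mg strata, so the tablet rows would need a similar look by tablet dose. Normalisation does not adjust for application site or time since application, so the result is not a pure measure of clearance.

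**Secondary option.** Cross sex or age with latest dose. This avoids the proportionality assumption, but the cells become small. Two age groups × three doses × two cohorts is 12 cells per visit. With the target of 100 subjects completing 52 weeks, an even spread would give 100/12, or about 8 per cell. No minimum number aged 65 or over is set, so those cells may be much smaller.

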10.1 SAS Code

Kaplan-Meier

```
Proc lifetest plots=survival(atrisk) outsurv=sdf;  
  Strata COHORT;  
  Time TTE*CENSOR(1);  
  Ods output quartiles=MST;  
* TTE is time to discontinuation (ie, the last dose date – the first dose date + 1);  
* If completer then CENSOR=1; else CENSOR=0;  
* SURVIVAL, SDF_LCL, SDF_UCL variables in OUTSURV dataset will be tabulated where the TTE  
is closest (and smaller) to 28 weeks (196 days) and 52 weeks (364 days);
```

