15.3.9 Interim analysis

Interim analysis to judge study continuation is not performed. However, for submission purpose, it might be conducted before final database lock.

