7.1.3 DSP-5423P patch duration

The treatment duration of DSP-5423P will be the one from the initial application date to the last application date of DSP-5423P. Termination of application (for any reason) will be an event and

completion of treatment will be a censor. That is to say, time to event based on treatment duration from start to termination of treatment will be analyzed. In this analysis, subjects who complete study treatment will be censored not as an event, considering those subjects can pursue study treatment even after treatment completion.

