9.11.4 Time to Treatment Discontinuation

All cause discontinuation of DSP-5423P is considered as an event and completion of DSP-5423P

application is considered as a censor, and Kaplan-Meier estimate for 50 percentiles and its 95% CI for time to event will be analyzed. Also the number and percentage of subjects who applied DSP-5423P for 28 weeks or 52 weeks will be summarized. Those analyses will be performed for each cohort overall and also by use of prior antipsychotics (Blonanserin and Other/None).

The final application date of DSP-5423P can be either event date or date of censored. Kaplan-Meier plots for each cohort will be provided. One for each cohort by use of prior antipsychotics will also be provided. Time to Treatment Discontinuation will be listed.

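### The Kaplan-Meier code makes every non-completer a discontinuation event; this is harmless at final lock but understates retention, mainly in cohort 2, if a pre-lock submission analysis includes subjects still on treatment

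*SAP*

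**What the plan says.** Three parts of the SAP define this endpoint.

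- **SAP 7.1.3** (event): "Termination of application (for any reason) will be an event and" (censoring): "completion of treatment will be a censor". It censors completers on the reasoning that they could have gone on with treatment.
- **SAP 9.11.4** repeats the two outcomes, beginning "All cause discontinuation of DSP-5423P is considered as an event and completion of DSP-5423P", and dates both at the last patch: "The final application date of DSP-5423P can be either event date or date of censored". It asks for the median with its confidence interval, and for the number and percentage of subjects treated for 28 and 52 weeks. All of this is by cohort.
- **SAP 10.1** gives the code. The time statement begins "Time TTE*CENSOR(1", so the value 1 means censored and anything else is an event. The flag is set by "If completer then CENSOR=1; else CENSOR=0", and the time variable is described as "TTE is time to discontinuation (ie, the last dose date – the first dose date + 1". The analysis is stratified by cohort.

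None of the three mentions a data cut-off date or a subject who is still applying patches.

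Protocol 15.3.9 rules out an interim analysis to decide on continuation, but adds that "for submission purpose, it might be conducted before final database lock". SAP section 3 records no change from the protocol's analyses, and the SAP gives no separate rule for such an analysis.

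**The concern.** The text and the code agree only when every subject has either completed or discontinued. For a subject still on treatment they part. By the text that subject has not had the event; by the code's "else" branch that subject has had it, on the last recorded application date. The SAP's own reason for censoring completers, that they could have continued, applies at least as strongly to someone who is in fact continuing.

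The protocol allows for an analysis at a time when such subjects may exist. Time to discontinuation is the only time-to-event effectiveness endpoint, and its curve, median and 28- and 52-week retention would all be affected.

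The error would also fall unevenly. Protocol 7.1 starts cohort 2 only after cohort 1 has finished enrolling, so ongoing subjects at any cut would sit mainly in cohort 2. Two cohorts with the same true retention could then look different. That would read as a contrast between subjects switched from the tablet and subjects started directly on the patch, and switching is a secondary objective.

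**Working it through.** **Inputs from the documents.** Patch treatment lasts 52 weeks (364 days). Enrolment runs from December 2014 to May 2016 and the study to July 2017 (protocol 7.4). The target is 200 subjects, because 100 with 52-week exposure are wanted and about half stopped early in previous tablet studies (protocol 15.1).

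**The plan's own figure.** 100 / (1 − 0.5) = 200, which reproduces the target. The point does not depend on it.

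**Assumptions not in the documents.** 100 subjects per cohort; even entry over 517 days (about December 2014 to May 2016), with cohort 1 in the first half (days 0 to 258.5) and cohort 2 in the second (days 258.5 to 517); a constant discontinuation rate; 50% true retention at 52 weeks in both cohorts; and ongoing subjects timed to their last application before the cut.

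**Formula.** Under the code nobody is censored before completion. The coded estimate at 52 weeks is therefore the share of subjects seen to reach it:

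coded retention = true retention × share of the cohort whose possible follow-up at the cut is at least 364 days.

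**Cohort 1.** The last entry is at day 258.5. With 6 weeks (42 days) of tablets first, the last completion is at 258.5 + 42 + 364 = day 664.5. Nobody is ongoing at day 700 or day 791, so the coded estimate is right, about 50%.

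**Cohort 2, cut at day 700.** Possible follow-up runs from 700 − 517 = 183 to 700 − 258.5 = 441.5 days.

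- Share with at least 364 days: (441.5 − 364) / 258.5 = 0.30.
- Coded 52-week retention: 0.50 × 0.30 = 0.15.
- Share still ongoing: (364 / ln 2) × (2^(−183/364) − 0.5) / 258.5 = 0.42.

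**Cohort 2, cut at day 791.** Possible follow-up runs from 274 to 532.5 days.

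- Share with at least 364 days: (532.5 − 364) / 258.5 = 0.65.
- Coded 52-week retention: 0.50 × 0.652 = 0.33.
- Share still ongoing, by the same formula with 274 in place of 183: 0.19.

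| Cut | Cohort 1, code | Cohort 2, code | Ongoing subjects censored, either cohort |
|---|---|---|---|
| Day 700 | about 50% | 15% | about 50% |
| Day 791 | about 50% | 33% | about 50% |
| After the last completion (517 + 364 = day 881) | about 50% | about 50% | about 50% |

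Simulated Kaplan-Meier curves give the same values to within about a percentage point.

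**Range.** The multipliers 0.30 and 0.652 do not depend on true retention. With 70% true retention, cohort 2 is coded as 21% (day 700) and 46% (day 791). With 40% it is coded as 12% and 26%.

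**Week 28.** The effect is smaller and goes first. At day 700 the share of cohort 2 with at least 196 days is (441.5 − 196) / 258.5 = 0.95. True retention is 0.5^(196/364) = 0.69, so the code gives about 0.65. At day 791 everyone in cohort 2 has at least 274 days and there is no error at week 28.

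**If ongoing subjects were left without a last dose date.** The procedure would drop them. Cohort 2 would then show 0.15 / (1 − 0.42) = 0.26 at day 700 and 0.326 / (1 − 0.19) = 0.40 at day 791. Both are still too low.

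**The case against.** The strongest reply is that the SAP is written for the locked database. Populations and important deviations are settled just before lock (SAP 6 and 9.3). By then every patched subject is a completer or a discontinuer, and a two-state rule is exact. That stands: there is no error at final lock.

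The trigger is also conditional. Protocol 15.3.9 says only that an analysis might be done. It gives no cut-off and no list of endpoints, and an analysis between the last subject's last visit and the lock would contain no ongoing subjects. A reader might infer that subjects will be miscounted in the submission, or that many will be mid-treatment at that analysis. The documents support neither statement.

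It can be argued further that the event definitions in 7.1.3 and 9.11.4 govern, and that the flag is only a comment in an appendix. By that reading ongoing subjects are an unaddressed case. This has some force, but the comment is the one instruction that says how to set the flag, and it contradicts those definitions for ongoing subjects. A prespecified rule should not rely on the programmer departing from it.

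Two cautions about the remedy also stand. Before lock, some true dropouts may not yet be recorded, and censoring everyone without a discontinuation record would bias retention upward. The crude 28- and 52-week percentages need their own rule.

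**Conclusion.** The point holds in conditional form. The code contradicts the SAP's event definition for subjects still on treatment, and seeing this needs no assumption. It affects results only if a pre-lock analysis includes time to discontinuation while subjects are ongoing. Retention is then understated, mainly in cohort 2.

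The sizes (15% and 33% against about 50% in cohort 2 at day 700 and day 791) are illustrative. They rest on assumed cohort sizes, even entry, a constant discontinuation rate and assumed cut dates. A single figure pooled over both cohorts would be misleading, because the planned curves are by cohort and the error is not shared equally between them.

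The primary objective, safety, is not touched. The endpoint is descriptive and the study is uncontrolled. The correction should be made because it is nearly free and the analysis at risk is one intended for a submission.

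**What to change.** 1. In SAP 10.1, set CENSOR=0 only for subjects with a documented DSP-5423P discontinuation. Set CENSOR=1 for completers and for subjects ongoing at the data cut-off, with time running to the last known application on or before the cut-off.
2. State the same in SAP 7.1.3 and 9.11.4, adding the ongoing category and the cut-off date.
3. Before any pre-lock analysis of this endpoint, reconcile each subject's disposition status at the cut-off, so that a dropout not yet recorded is not censored as ongoing.
4. At such an analysis, limit the crude 28- and 52-week percentages to subjects who could have reached that time by the cut-off.

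The cost is one line of code, a short addition in two SAP sections, and a disposition check if the early analysis is done. The final-lock result is unchanged.
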